6.4. WINDOWING CONVENTIONS

No visit windows will be applied in this study and the scheduled assessments will be reported and analyzed as per eCRF collection.

Document: Z:\RPL554\AZA40375\Biostatistics\Documentation\SAP\Verona RPL554-DP-201 SAP v2.0 – Part B

Author: [name] / [name]

Version Number: 2.0

Version Date: [08JUL2019]

Template No.: CS_TP_BS016 Revision 5

Reference: CS_WI_BS005

Effective Date: 01Apr2018

Copyright © 2009, 2010, 2012, 2016, 2018 IQVIA. All rights reserved. The contents of this document are confidential and proprietary to IQVIA Holdings Inc. and its subsidiaries. Unauthorized use, disclosure or reproduction is strictly prohibited.

6.5. STATISTICAL TESTS

The default significant level will be (5%); confidence intervals will be 95% and all tests will be 2-sided, unless otherwise specified in the description of the analyses. All significant p-values (i.e. < 5%) will be flagged by means of a “*” for ease of review.

For presentation of summary statistics for quantitative and qualitative variables see [Appendix 1](#); Programming conventions for outputs.

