9.3.2.2 Secondary Endpoints

- Safety and tolerability:
 - Continuous monitoring of adverse events
 - Laboratory safety tests (hematology, blood chemistry and urinalysis)
 - 12-lead ECG (including QTcF and heart rate), supine vital signs (blood pressure and pulse rate)
- Change from baseline in (morning) trough FEV₁ measured prior to morning dosing on Day 7
- Change from baseline in peak FEV₁ measured after first dose
- Change from baseline in average FEV₁ AUC_{0-4h} measured after morning dosing on Day 7
- Change from baseline in average FEV₁ AUC_{0-12h} measured after first dose and after morning dosing on Day 7
- Determination of onset of action (>10% increase in FEV₁ from pre- to post- first dose, censored at 120 minutes) after first dose
- RPL554 steady state pharmacokinetics (AUC_{0-12h}, C_{max}, t_{max}, accumulation ratio) after dose 13 on Day 7
- Change from baseline in peak pulse after first dose on Day 1 and after morning dosing on Day 7
- Change from baseline in average FEV₁ AUC_{0-4h} and average FEV₁ AUC_{0-12h} on Day 1
- Change from baseline in rescue medication use

9.3.2.3 *Exploratory Endpoint*

- Evaluation of dose response of RPL554 on peak and average FEV₁ AUC_{0-12h} after morning dose on Day 7, and morning trough FEV₁ prior to the last dose on Day 7
- Change from baseline in Likert dyspnea scale measured after single dose and after morning dose on Day 7

9.4 *Statistical Methods*

In general, unless stated otherwise, continuous variables will be summarized using descriptive statistics (number of patients, mean, standard deviation, median, minimum and maximum values) and for categorical (nominal) variables, the number and percentage of patients will be used.

All hypothesis testing will be done using two-sided alternative hypotheses. P-values less than 5% will be considered statistically significant.

9.4.1 *Patient Disposition*

The number of patients enrolled, randomized, completed or withdrawn (with reason for withdrawal) will be summarized.

9.4.2 *Protocol Deviations*

All protocol deviations collected will be divided into critical, major or minor categories. Prior to database lock protocol deviations will be reviewed and consequences for inclusion of patients in various analysis population sets determined and documented.

9.4.3 *Demographics and Other Baseline Characteristics*

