7.4. MULTIPLE COMPARISONS/ MULTIPLICITY

Significance of treatment effect will be tested for the primary and secondary efficacy endpoints in Part A and will be done for each of the doses of RPL554 against placebo, starting with the highest dose (6000 µg). To this end, the fixed-sequence testing approach (Maurer et al., 1995; Westfall & Krishen, 2001) will be used.

For the endpoints, let $i = 0, 1, 2, 3, 4$ and 5 represent increasing dose levels, 0 denoting placebo. Also, let μ_i , $i = 0, 1, 2, 3, 4$ and 5 denote the mean change from baseline for the endpoint of interest for placebo and each increasing active dose level, respectively. The null hypotheses are defined as: $H_i: \mu_j - \mu_0 = 0$ and will be tested against the 2-sided alternative $K_i: \mu_j - \mu_0 \neq 0$, $j = 1, 2, 3, 4$ and 5 .

Finally, let p_1, p_2, p_3, p_4, p_5 denote the marginal p-values obtained from the statistical tests associated with H_1, H_2, H_3, H_4, H_5 (obtained from the model).

The fixed-sequence testing will begin with the null hypothesis corresponding to the highest dose versus placebo. If a statistically significant difference is found at the 2-sided α level of 5%, the testing will proceed with the next highest dose. Otherwise, testing stops, and the remaining null hypotheses are considered as failed to reject, without testing.

This testing strategy can be written as the following stepwise algorithm:

- Step 1: If $p_5 \leq \alpha$ reject H_5 and go to Step 2. Otherwise, fail to reject H_5, H_4, H_3, H_2 and H_1 and stop.
- Step 2: If $p_4 \leq \alpha$ reject H_4 and go to Step 3. Otherwise, fail to reject H_4, H_3, H_2 and H_1 and stop.
- Step 3: If $p_3 \leq \alpha$ reject H_3 and go to Step 4. Otherwise, fail to reject H_3, H_2 and H_1 and stop.
- Step 4: If $p_2 \leq \alpha$ reject H_2 and go to Step 5. Otherwise, fail to reject H_2 and H_1 and stop.
- Step 5: If $p_1 \leq \alpha$ reject H_1 . Otherwise, accept H_1 .

The fixed-sequence procedure controls the family-wise error rate in the strong sense because, for each null

Document: Z:\RPL554\AZA40375\Biostatistics\Documentation\SAP\Verona RPL554-DP-201 SAP v1.0 – Part A

Author: [name]

Version Number: 1.0

Version Date: [19DEC2018]

Template No.: CS_TP_BS016 Revision 5

Reference: CS_WI_BS005

Effective Date: 01Apr2018

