7.4. MULTIPLE COMPARISONS/ MULTIPLICITY

Significance of treatment effect will be tested for the primary and secondary efficacy endpoints in Part B and will be done for each of the doses of RPL554 against placebo, starting with the highest dose (3000 µg). To this end, the fixed-sequence testing approach (Maurer et al., 1995; Westfall & Krishen, 2001) will be used.

For the endpoints, let $i = 0, 1, 2, 3$ and 4 represent increasing dose levels, 0 denoting placebo. Also, let μ_i , $i = 0, 1, 2, 3$ and 4 denote the mean change from baseline for the endpoint of interest for placebo and each increasing active dose level, respectively. The null hypotheses are defined as: $H_i: \mu_j - \mu_0 = 0$ and will be tested against the 2-sided alternative $K_i: \mu_j - \mu_0 \neq 0$, $j = 1, 2, 3$ and 4 .

Finally, let p_1, p_2, p_3, p_4 denote the marginal p-values obtained from the statistical tests associated with H_1, H_2, H_3, H_4 (obtained from the model).

The fixed-sequence testing will begin with the null hypothesis corresponding to the highest dose versus placebo. If a statistically significant difference is found at the 2-sided α level of 5%, the testing will proceed with the next highest dose. Otherwise, testing stops, and the remaining null hypotheses are considered as failed to reject, without testing.

This testing strategy can be written as the following stepwise algorithm:

- Step 1: If $p_4 \leq \alpha$ reject H_4 and go to Step 2. Otherwise, fail to reject H_4, H_3, H_2 and H_1 and stop.
- Step 2: If $p_3 \leq \alpha$ reject H_3 and go to Step 3. Otherwise, fail to reject H_3, H_2 and H_1 and stop.
- Step 3: If $p_2 \leq \alpha$ reject H_2 and go to Step 4. Otherwise, fail to reject H_2 and H_1 and stop.
- Step 4: If $p_1 \leq \alpha$ reject H_1 . Otherwise, accept H_1 .

Document: Z:\RPL554\AZA40375\Biostatistics\Documentation\SAP\Verona RPL554-DP-201 SAP v2.0 – Part B

Author: [name] / [name]

Version Number: 2.0

Version Date: [08JUL2019]

Template No.: CS_TP_BS016 Revision 5

Reference: CS_WI_BS005

Effective Date: 01Apr2018

Copyright © 2009, 2010, 2012, 2016, 2018 IQVIA. All rights reserved. The contents of this document are confidential and proprietary to IQVIA Holdings Inc. and its subsidiaries. Unauthorized use, disclosure or reproduction is strictly prohibited.

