The fixed-sequence procedure controls the family-wise error rate in the strong sense because, for each null hypothesis, the testing is conditional upon rejecting all hypotheses earlier in the sequence (Dmitrienko, et al., 2009).

Each secondary endpoint will be tested independently and nominally following a hierarchical testing of doses like the one used for the primary endpoint.

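### In the Part B SAP the significance star follows p < 5% alone, so it can mark a dose that the fixed-sequence rule counts as not rejected

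*SAP*

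**What the plan says.** Two definitions of significance stand side by side.

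- **By p-value alone.** SAP Part B 6.5: "All significant p-values (i.e. < 5%) will be flagged by means of a" star, as an aid to review. The sentence before it sets the level: "The default significant level will be (5%); confidence intervals will be 95% and all tests will be 2-sided". Protocol 9.4: "P-values less than 5% will be considered statistically significant". None of these mentions the dose order.
- **By position in a sequence.** SAP Part B 7.4 begins with 3000 µg against placebo and goes to the next lower dose only after a rejection: "Otherwise, testing stops, and the remaining null hypotheses are considered as failed to reject, without testing". Protocol 9.4.5 sets the same top-down order. Section 7.4 rests its error claim on that condition: "The fixed-sequence procedure controls the family-wise error rate in the strong sense". Secondary endpoints keep the dose order within each endpoint: "Each secondary endpoint will be tested independently and nominally following a hierarchical testing of doses like the one used for the primary endpoint".

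The model code in 15.1.3 and 15.2.3.1 requests all pairwise treatment differences in one call, so a p-value exists for every dose whatever the sequence has decided. Appendix 1 fixes only how p-values are rounded and displayed. No section limits the star to hypotheses rejected in sequence or labels the later p-values as nominal. The Part A SAP has the same text in its 6.5 and 7.4, with five doses from 6000 µg down.

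**The concern.** Suppose 3000 µg gives p above 0.05 on peak FEV₁ and 1500 µg gives p = 0.03. Under 6.5 the 1500 µg result is significant and starred. Under 7.4 its null hypothesis was never tested and counts as not rejected. A programmer who follows 6.5 as written prints a significance mark that the multiplicity section does not allow.

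This matters most for the Part B primary table. Section 15.1.3 states the aim as showing that at least one of the four doses improves peak FEV₁ over placebo, and the stars by dose are where a reader will look for that answer. The stars carry only a per-test 5% level, whereas the sequence carries a 5% level across the doses.

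**Working it through.** **Inputs.** Protocol 9.5: residual CV 6%, 30 patients, 80% power for a 4.6% pairwise difference, baseline FEV₁ 1.5 L. SAP Part B 6.5: two-sided 5%. SAP Part B 7.4: four dose-placebo hypotheses ("Finally, let p_1, p_2, p_3, p_4 denote the marginal p-values obtained from the statistical tests"). The documents give no effect by dose for this formulation, so the dose patterns below are assumptions.

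**Step 1: reproduce the plan's own figure.** On the log scale:
- σ = √ln(1 + 0.06²) = 0.0599
- SE of a within-patient difference = σ√(2/30) = 0.0155
- difference = ln(1.046) = 0.0450, so difference/SE = 2.91
- noncentral t with 29 df gives power 80.2%; the detectable difference at 80% is 4.59%
- 4.6% × 1.5 L = 69 mL, matching the stated 70 mL or so

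The crossover residual df, 149 − 29 − 4 − 4 = 112, gives 82.1%; a normal approximation gives 82.8%. The design figure reproduces.

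**Step 2: compare the two rules.** One million trials were simulated per pattern, with four doses sharing one placebo mean, n = 30 and 112 residual df (111 with the baseline covariate makes no material difference):

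t_j = (mean_j + δ_j − mean_placebo) / (s√(2/30))

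- Star rule: star dose j if |t_j| exceeds the 5% critical value.
- Sequence rule: reject dose j only if it and every higher dose exceed it.
- Contradiction: at least one dose is starred but not rejected in sequence.

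| Assumed true effects (150 to 3000 µg) | A star contradicts the sequence | 3000 µg misses and a lower dose is starred |
|---|---|---|
| No effect | 11.7% | 10.4% |
| Rising in quarters (log scale) to 4.6% | 14.6% | 5.8% |
| All doses 4.6% | 29.3% | 15% |
| All doses 6.9% | about 3% | about 1% |

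The 6.9% row takes 103 mL / 1.5 L, from the nebulized 1.5 mg result given on top of tiotropium in protocol 1.1. That is another formulation and setting, used here only to show a larger effect. With 36 patients instead of 30, the 29.3% becomes 21.3%.

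**Step 3: false stars under the global null.** At least one dose-placebo star appears in 15.4% of trials. The sequence rejects anything in 5.0%, since nothing can be rejected unless 3000 µg is rejected first. As a check, four independent tests would give 1 − 0.95⁴ = 18.5%; sharing a placebo lowers this to 15.4%. The difference, 15.4% − 5.0% = 10.4%, is the null-row entry in the last column.

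**Step 4: after the change.** If the star is limited to sequence rejections, the chance of any false dose-placebo star under the global null is 5.0%.

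**The case against.** The strongest reply is that 6.5 is a display convention. It is offered for ease of review under a default level, 7.4 calls the model outputs marginal p-values, and the decision algorithm in 7.4 is explicit. That stands as far as error control goes. A reader might infer that the stars break the family-wise control claimed in 7.4. They do not: the claim belongs to the sequential procedure, which 6.5 leaves alone, and 6.5 promises only a per-test level. But the reply does not reconcile the wording. The star sentence itself defines significant as below 5%, and the proviso allowing other specifications is attached to the preceding sentence on level, intervals and sidedness.

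Three larger readings are also tempting and not supported:

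- **Counting dose-dose contrasts.** Including them raises the null chance of some star in Part B to 28%. Protocol 9.4.5 makes those comparisons secondary and they were never in the sequence, so their stars cannot contradict it.
- **Reading 29% as a false-positive rate.** That pattern assumes every dose works, so each star marks a true effect. It measures disagreement between two rules, and it assumes 150 µg works as well as a dose 20 times larger.
- **Giving Part A equal weight.** Its null figure is 17.8% against 5.0%, but its primary endpoints are pharmacokinetic, FEV₁ is secondary and nominal, and the protocol amendment says Part A is complete. No confirmatory claim depends on its stars.

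Finally, section 8 leaves table content to templates that are not in the documents. A footnote calling the stars nominal may exist there, so what the tables will show is not certain. The SAP text would still disagree with itself.

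**Conclusion.** The conflict is real and lies in the text: SAP Part B 6.5 and protocol 9.4 against SAP Part B 7.4 and protocol 9.4.5. Followed as written, 6.5 can mark as significant a dose whose null hypothesis the plan treats as not rejected. With no true effect, some dose-placebo star appears in about 15% of Part B trials against 5% for the sequence. The chance of a contradicting star runs from about 3% to 29% over the patterns tried. These figures assume complete data on 30 patients, equal residual variance, CV 6% and the chosen dose effects. The issue concerns how results are marked and read; the testing procedure itself is sound. It is worth correcting because it touches the primary table and the correction is cheap.

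**What to change.** In SAP Part B 6.5, replace the star rule. For each endpoint tested under the 7.4 hierarchy, star a dose-placebo p-value only if it and the p-values of all higher doses for that endpoint are ≤ 0.05. Apply this to the primary endpoint and to each secondary endpoint within its own dose order, with the secondary results labelled nominal across endpoints. Print all other p-values, including dose-dose contrasts, unstarred or with a distinct nominal mark. Using ≤ 0.05 also removes the small mismatch between < 5% in 6.5 and ≤ α in 7.4.

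In protocol 9.4, add to the significance sentence: subject to the sequential procedure in 9.4.5.

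For Part A, leave the executed SAP as it is and state in the study report that its stars are nominal.

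The cost is SAP and protocol wording, one programming rule, and fewer stars in the tables.

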6.6. COMMON CALCULATIONS

Assessments assigned to treatment periods:

- Based on the day of assessment relative to the start date of each treatment period as defined by the first treatment administration for that specific treatment period:
 - Treatment period 1
 - Treatment period 2
 - Treatment period 3
 - Treatment period 4
 - Treatment period 5

For quantitative measurements, change from baseline will be calculated as:

- Test value at post-dose timepoint – baseline value.

For quantitative measurement values of FEV₁ and FEV₁ AUCs will be calculated based on:

- The highest FEV₁ reading from each assessment.
- The baseline value (average of the two pre-dose values [at 1-hour {±5 minutes} and immediately {within 5 minutes} } pre-dose) must be within ± 20% of the pre-albuterol value at Screening; otherwise, the patient will be a screen failure.

Peak effect will be calculated as:

- Maximum value in the first 4 hours after dosing.

Average effect will be calculated as:

- FEV₁ AUC divided by the length of the time interval of interest.

Document: Z:\RPL554\AZA40375\Biostatistics\Documentation\SAP\Verona RPL554-DP-201 SAP v2.0 – Part B

Author: [name] / [name]

Version Number: 2.0

Version Date: [08JUL2019]

Template No.: CS_TP_BS016 Revision 5

Reference: CS_WI_BS005

Effective Date: 01Apr2018

Copyright © 2009, 2010, 2012, 2016, 2018 IQVIA. All rights reserved. The contents of this document are confidential and proprietary to IQVIA Holdings Inc. and its subsidiaries. Unauthorized use, disclosure or reproduction is strictly prohibited.

Log-transformations will be performed on FEV₁ data:

- FEV₁ will be analyzed using multiplicative models, which means that data will be logged prior to analysis. The results will then be back-transformed to linear scale (treatment differences will thus be ratios of geometric means).

6.7. SOFTWARE VERSION

All analyses will be conducted using SAS version 9.4.

7. STATISTICAL CONSIDERATIONS

7.1. ADJUSTMENTS FOR COVARIATES AND FACTORS TO BE INCLUDED IN ANALYSES

The following covariates are used in the analyses. For details of their inclusion in the models, see the specific analysis section.

- Randomized treatment (fixed).
 - RPL554 150µg
 - RPL554 500µg
 - RPL554 1500µg
 - RPL554 3000µg
 - Placebo
- Treatment period (fixed).
 - Treatment period 1
 - Treatment period 2
 - Treatment period 3
 - Treatment period 4
 - Treatment period 5
- Baseline value of analyzed variable (covariate).

Document: Z:\RPL554\AZA40375\Biostatistics\Documentation\SAP\Verona RPL554-DP-201 SAP v2.0 – Part B

Author: [name] / [name]

Version Number: 2.0

Version Date: [08JUL2019]

Template No.: CS_TP_BS016 Revision 5

Reference: CS_WI_BS005

Effective Date: 01Apr2018

Copyright © 2009, 2010, 2012, 2016, 2018 IQVIA. All rights reserved. The contents of this document are confidential and proprietary to IQVIA Holdings Inc. and its subsidiaries. Unauthorized use, disclosure or reproduction is strictly prohibited.

7.2. MULTICENTER STUDIES

This study is being conducted at 1 study center in the US.

7.3. MISSING DATA

Missing safety data will not be imputed, apart from partial date imputations as specified in [Appendix 2](#).

Missing efficacy data will be handled as described in [Section 15.1.2](#) and [Section 15.2.2](#) of this SAP.

7.4. MULTIPLE COMPARISONS/ MULTIPLICITY

Significance of treatment effect will be tested for the primary and secondary efficacy endpoints in Part B and will be done for each of the doses of RPL554 against placebo, starting with the highest dose (3000 µg). To this end, the fixed-sequence testing approach (Maurer et al., 1995; Westfall & Krishen, 2001) will be used.

For the endpoints, let $i = 0, 1, 2, 3$ and 4 represent increasing dose levels, 0 denoting placebo. Also, let μ_i , $i = 0, 1, 2, 3$ and 4 denote the mean change from baseline for the endpoint of interest for placebo and each increasing active dose level, respectively. The null hypotheses are defined as: $H_i: \mu_j - \mu_0 = 0$ and will be tested against the 2-sided alternative $K_i: \mu_j - \mu_0 \neq 0$, $j = 1, 2, 3$ and 4 .

Finally, let p_1, p_2, p_3, p_4 denote the marginal p-values obtained from the statistical tests associated with H_1, H_2, H_3, H_4 (obtained from the model).

The fixed-sequence testing will begin with the null hypothesis corresponding to the highest dose versus placebo. If a statistically significant difference is found at the 2-sided α level of 5%, the testing will proceed with the next highest dose. Otherwise, testing stops, and the remaining null hypotheses are considered as failed to reject, without testing.

This testing strategy can be written as the following stepwise algorithm:

- Step 1: If $p_4 \leq \alpha$ reject H_4 and go to Step 2. Otherwise, fail to reject H_4, H_3, H_2 and H_1 and stop.
- Step 2: If $p_3 \leq \alpha$ reject H_3 and go to Step 3. Otherwise, fail to reject H_3, H_2 and H_1 and stop.
- Step 3: If $p_2 \leq \alpha$ reject H_2 and go to Step 4. Otherwise, fail to reject H_2 and H_1 and stop.
- Step 4: If $p_1 \leq \alpha$ reject H_1 . Otherwise, accept H_1 .

Document: Z:\RPL554\AZA40375\Biostatistics\Documentation\SAP\Verona RPL554-DP-201 SAP v2.0 – Part B

Author: [name] / [name]

Version Number: 2.0

Version Date: [08JUL2019]

Template No.: CS_TP_BS016 Revision 5

Reference: CS_WI_BS005

Effective Date: 01Apr2018

Copyright © 2009, 2010, 2012, 2016, 2018 IQVIA. All rights reserved. The contents of this document are confidential and proprietary to IQVIA Holdings Inc. and its subsidiaries. Unauthorized use, disclosure or reproduction is strictly prohibited.

The fixed-sequence procedure controls the family-wise error rate in the strong sense because, for each null hypothesis, the testing is conditional upon rejecting all hypotheses earlier in the sequence (Dmitrienko, et al., 2009).

Each secondary endpoint will be tested independently and nominally following a hierarchical testing of doses like the one used for the primary endpoint.

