2.2.2 Secondary Objectives

- To investigate the safety and tolerability of repeat doses of RPL554, administered by DPI
- To investigate the bronchodilator effect of RPL554 administered by DPI, in terms of average FEV₁ AUC_{0-4h}, average FEV₁ AUC_{0-12h} and trough FEV₁
- To determine the onset of action of RPL554 administered by DPI
- To evaluate the PK profile of RPL554 administered by DPI
- To evaluate the amount of rescue medication use during treatment periods

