9.4.5 Efficacy/Pharmacodynamics

FEV₁ and FVC will be summarized as actual value and change from baseline using descriptive statistics over time for all treatments and both study parts.

The peak effect on FEV₁ during these time intervals will be computed as the maximum value in the 4 hours after dosing. The average effect (average FEV₁ AUC_{0-t}) will be calculated as the AUC divided by the length of the time interval of interest. For analysis of the peak, average and trough FEV₁, the change from baseline will be expressed as the parameter divided by the pre-dose Day 1 baseline value.

In Part A, computed pharmacodynamic parameters for FEV₁ will be compared between the treatments using analysis of covariance models with fixed factor treatment, and using the pre-dose baseline value as a covariate. In Part B, computed pharmacodynamic parameters (peak, AUC₀₋₄, AUC₀₋₁₂ and trough) for FEV₁ will be compared between the treatments using analysis of covariance models adjusting for treatment period and patient, and using the pre-dose Day 1 baseline value as a covariate. FEV₁ will be analyzed using multiplicative models, which means that data (dependent and baseline) are logged prior to analysis and the result then transformed back to the linear scale giving treatment differences as ratios of geometric means.

Primarily, active treatments will be compared to placebo. For RPL554 DPI, the high dose will first be compared to placebo, and if found statistically significant then the next lower dose will be compared to placebo, and if found statistically significant then the subsequent lower dose will be compared to placebo, and this procedure repeated for all doses. Secondarily, the different doses of RPL554 DPI will be compared. Results of the comparisons will be expressed as the mean geometric ratio with 95% confidence intervals and associated, 2-sided, p-value.

Onset of action will be calculated and summarized by treatment. In Part B, a Kaplan-Meier plot illustrating time to onset will be constructed and from the survival curves the median time to onset will be estimated. Placebo will not be included in summaries of onset of action.

In Part B, the average use of rescue medication during the treatment periods will be summarized by treatment group. In addition, all rescue medication used during the treatment visits (Day 1 in Part A and Days 1 and 7 in Part B) will be listed to assess the accuracy of the FEV₁ recordings.

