Copyright © 2009, 2010, 2012, 2016, 2018 IQVIA. All rights reserved. The contents of this document are confidential and proprietary to IQVIA Holdings Inc. and its subsidiaries. Unauthorized use, disclosure or reproduction is strictly prohibited.

accompanying figure will not be presented. Patients receiving placebo will not be summarized in either tables or figure.

15.2.1.4. RPL554 steady state pharmacokinetics (AUC_{0-12h}, Cmax, time to maximum concentration [tmax]) (Secondary variable 8)

Concentration of RPL554 and computed PK parameters (AUC_{0-12h}, C_{max} [maximum concentration], t_{max} [time to maximum concentration]) on Day 7 of each treatment period (pre-dose, 30 minutes and 1, 1.5, 2, 4, 8 and 12-hours post dose).

15.2.1.5. Change from baseline in rescue medication use during treatment periods (Secondary variable 9)

The average use, in terms of weight (mcg) of rescue medication during the treatment periods will be collected from the Rescue Medication Canister Dispensed and Rescue Medication Canister Weight eCRF pages and will be summarized by treatment group. Rescue medication used will be calculated from the difference in weight at time of dispensing and weight at time of collection. So, change from baseline is the difference in rescue medication from baseline (at pre-dose on Day 1) and the collection visit (12hr post-dose on Day 7).

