Summary statistics of change from baseline will be presented at Days 1 to 7 of each treatment period by treatment group. In addition, all rescue medication used during the serial spirometry assessments(Days 1 and 7) will be listed to assess the accuracy of the FEV₁ recordings.

Document: Z:\RPL554\AZA40375\Biostatistics\Documentation\SAP\Verona RPL554-DP-201 SAP v2.0 – Part B

Author: [name] / [name]

Version Number: 2.0

Version Date: [08JUL2019]

Template No.: CS TP BS016 Revision 5

Reference: CS WI BS005

Effective Date: 01Apr2018

Copyright © 2009, 2010, 2012, 2016, 2018 IQVIA. All rights reserved. The contents of this document are confidential and proprietary to IQVIA Holdings Inc. and its subsidiaries. Unauthorized use, disclosure or reproduction is strictly prohibited.

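### SAP Part B 7.4 promises a dose-against-placebo test for each secondary efficacy endpoint, but rescue use gets only summaries by treatment group, with no within-patient estimate, confidence interval or p-value

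*SAP*

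**What the plan says.** SAP Part B 7.4 sets the scope of testing: "Significance of treatment effect will be tested for the primary and secondary efficacy endpoints in Part B". Each dose is compared with placebo in fixed sequence from 3000 µg downwards, at two-sided 5%, using p-values taken from the model. It then adds: "Each secondary endpoint will be tested independently and nominally following a hierarchical testing of doses".

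Rescue use is a Part B secondary objective in protocol 2.2.2 ("To evaluate the amount of rescue medication use during treatment periods") and a secondary endpoint in protocol 9.3.2.2 ("Change from baseline in rescue medication use"). SAP 15.2.1.5 lists it under secondary efficacy as variable 9.

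For its analysis, SAP 15.2.3.4 says only: "Summary statistics of change from baseline will be presented at Days 1 to 7 of each treatment period by treatment group". It adds a listing of rescue use on the spirometry days. Protocol 9.4.5 is descriptive too: "In Part B, the average use of rescue medication during the treatment periods will be summarized by treatment group".

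The crossover mixed model in SAP 15.2.3.1 (treatment, period, log baseline, random patient) covers secondary variables 1 to 6 only.

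**The concern.** A programmer cannot follow both 7.4 and 15.2.3.4 for rescue use. The first calls for a model-based p-value for each dose against placebo; the second provides no model, contrast or interval.

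The omission is also out of line with the rest of the plan. Exploratory dyspnea (SAP 15.3.3) and peak pulse, analysed under safety (SAP 16.4), each get an ANCOVA adjusting for treatment, period and patient. A named secondary efficacy endpoint gets less, although protocol 3.2 justifies the crossover by comparisons within patients.

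What is at stake is how the rescue result can be read. With group means and SDs alone, the report shows roughly how far apart doses and placebo were, but not how precisely that difference is known. A reader who judges it from the tabulated SDs would be using between-patient spread that a within-patient contrast removes.

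**Working it through.** **Plan's own figure.** The only precision figure in the documents is for peak FEV₁ (protocol 9.5): 30 patients, residual CV 6%, 80% power for a 4.6% difference. On the log scale, σ = √ln(1 + 0.06²) = 0.0599, SE = 0.0599 × √(2/30) = 0.0155 and δ = ln(1.046) = 0.0450. A paired t-test with 29 df gives power 80.2%, so the figure reproduces. It says nothing about rescue use, for which no SD, correlation or target difference is given.

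**Scope of 7.4 against the nine secondary variables (SAP 15.2.3).**

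| Variables | Planned analysis | Dose vs placebo test |
|---|---|---|
| 1–6 (FEV₁ measures) | Mixed model | Yes |
| 7 (onset) | Kaplan-Meier; doses compared with 3000 µg; placebo excluded | No |
| 8 (PK) | Third party, outside this SAP | No |
| 9 (rescue use) | Summary statistics and listing | No |

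Six of nine variables fit 7.4. Of the other three, rescue use is the one where a placebo contrast is available and simply not specified.

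**What the group table does give.** In patients with all five periods, the difference between two treatment means is the mean within-patient difference: (1/n)ΣY(dose) − (1/n)ΣY(placebo) = (1/n)Σ[Y(dose) − Y(placebo)]. So a point difference can be read off. It becomes approximate when patients are incomplete. The full analysis set admits patients with two periods (SAP 5.4), and protocol 4.3.4 expects about 36 randomized for 30 completers, so about 6 may be incomplete. Period effects need not cancel either, since 36 patients cannot be spread equally over 10 sequences (36/10 = 3.6).

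**What it does not give.** Take n = 30 complete patients, work in units of the total SD of per-period use, and let ρ be the within-patient correlation (assumed).

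- Independent-groups reading: SE = √(2/30) = 0.258; 95% half-width with 58 df = 0.52.
- Within-patient: SE = √(2(1 − ρ)/30); reduction = 1 − √(1 − ρ). For a model with treatment, period and patient, residual df = 150 − 1 − 29 − 4 − 4 = 112.

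| ρ (assumed) | Paired SE | Reduction in SE | 95% half-width (112 df) |
|---|---|---|---|
| 0.3 | √(1.4/30) = 0.216 | 16% | 0.43 |
| 0.5 | √(1.0/30) = 0.183 | 29% | 0.36 |
| 0.7 | √(0.6/30) = 0.141 | 45% | 0.28 |
| 0.8 | √(0.4/30) = 0.115 | 55% | 0.23 |

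**Is the variable ready to be modelled?** Not yet. SAP 12 takes canister weight from the end of Day 1 to the start of Day 7. SAP 15.2.1.5 takes it from pre-dose on Day 1 to 12 hours post-dose on Day 7. Protocol Table 6 and sections 6.4.1.3 and 6.4.2.1 schedule weighing after dosing on Day 1 and pre-dose on Day 7; none is scheduled after the Day 7 dose. A weight difference within a period is also an amount used, not a change from a baseline rate, despite the endpoint's label.

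**The case against.** The strongest reply is that 7.4 is loosely worded and nothing planned is missing. The two specific texts, protocol 9.4.5 and SAP 15.2.3.4, agree that rescue use is descriptive. The objective is to evaluate the amount used, not to compare doses with placebo. Section 7.4 draws its p-values from a model, and variable 9 has none. On this view, limiting 7.4 to variables 1–6 is the whole repair.

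Much of this stands. A reader might infer that the SAP breaches the protocol; it does not, because 15.2.3.4 matches 9.4.5 and 7.4 is the text that overreaches. A reader might also infer that the table cannot show how large a difference was, or that between-patient spread hides it; the means in complete patients show it approximately, and spread affects precision, not the difference in means. Nor can rescue use be called the only patient-driven measure covering the full week: the scheduled weighings leave out much of Days 1 and 7, and adverse events reported spontaneously by patients are recorded throughout.

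The standard-error comparison is open to challenge too, because no independent-groups test is planned and the correlation is unknown.

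What does not stand is leaving the text as it is. SAP 7.4 says each secondary endpoint will be tested, and narrowing it alone would still leave a secondary endpoint with a weaker analysis than exploratory dyspnea.

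**Conclusion.** The point holds as an inconsistency within SAP Part B and a missed estimate. Section 7.4 promises a placebo comparison that 15.2.3.4 does not deliver for rescue use, and that also does not fit onset or PK. No period-adjusted within-patient difference, confidence interval or p-value is planned for variable 9.

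The reduction in standard error is 16% to 55% for ρ from 0.3 to 0.8, against an independent-groups reading. That range rests on the assumed correlation and on 30 complete patients; it is not a loss the documents establish. With no SD for rescue use, nothing shows whether the resulting interval would be clinically informative.

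A reader might infer that the trial's error control is compromised. The documents do not support that: secondary tests are nominal under 7.4, and the primary endpoint, the modelled secondary endpoints and the sample size are untouched. The change is worth making because it is cheap, but it is not critical.

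**What to change.** Before Part B is unblinded:

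1. Reconcile SAP 12 and 15.2.1.5 with the protocol's weighing times (end of Day 1 and pre-dose on Day 7). Define the variable as amount used per treatment period, and state openly that this replaces a change-from-baseline label.
2. In SAP 15.2.3.4, add an additive mixed model with treatment and period as fixed factors and patient as random, without a baseline term. Report each dose minus placebo with 95% CI and nominal p-value in the 7.4 order. Always show a paired Wilcoxon signed-rank result as a sensitivity analysis, so that its use does not depend on how skewed the data look. Keep the descriptive table and listing.
3. Limit the scope wording of 7.4 to the primary endpoint and the secondary variables that have a placebo comparison: 1–6, and 9 once modelled. Record the added comparison in SAP 3.3, which now declares no change from the protocol.

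If the sponsor prefers description only, step 3 restricted to variables 1–6 removes the contradiction but leaves rescue use without a stated precision; step 1 is needed either way.

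The cost is SAP wording and a modest adaptation of the 15.1.3 code (no log transformation, no baseline term) on data already due to be collected. The downside is one more nominal, unpowered comparison, which should be labelled as such.
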